Our growth mindset intervention may also benefit academic performance, and our partner school, at its discretion, may be able to integrate it into part of their standard curriculum following the completion of the study. However, our specific research question is whether the chatbot interaction yields measurable improvements in youth mental health. Given the preponderance of AI chatbots aiming to address various aspects of mental health, such measurement is as important as it is rare. This study will contribute to the growing evidence base on how technology can inform and support youth mental health.

9b. Explanation for choice of comparator

Guided by discussions with the partner school, the control group will undertake alternate classroom activities assigned by the teacher (i.e., treatment as usual) during the intervention periods. The exact activity assigned to the control group will be recorded and reported. The control group will also receive a shortened version of the intervention after 7 weeks. At 7 weeks, all students will receive a printed booklet containing the full content of the intervention.

10. Objectives

The primary objective is to assess the effect of a brief, AI-guided growth mindset training on anxiety and depressive symptoms in youth in India, compared to usual classroom activities, from baseline to 3- and 7-weeks post-intervention. Key secondary objectives include assessing the acceptability of the intervention, assessing the effects on growth mindset beliefs and understanding patterns of engagement with the AI chatbot.

Methods: Patient and public involvement, trial design

11. Patient and public involvement

Inputs from the school partner were vital in developing and refining the intervention content. Critical feedback on the chatbot was provided across three one-hour sessions: (i) by three school teachers, (ii) by two fifth-grade students, and (iii) by a recent 12th grade graduate and a parent of that graduate (all linked to the partner school). These sessions also helped to generate some of the role-playing scenarios that are featured in the chatbot.

12. Trial design

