It is unlikely that participants will become distressed when completing this study and, given that none of the survey questions directly asks about intention to harm oneself or others, such content would not fit into the structure of the intervention or surveys. Nonetheless, if a student should describe mental health distress or an intent to harm themselves or others in the interface to the AI chatbot, the chatbot will respond with empathy and encourage them to call India's national mental health helpline (called TeleMANAS, reachable at [name].). As described in Section 15 (Intervention and Comparator), we have extensively tested the chatbot and are confident that its responses will be appropriate for a school setting. Nonetheless, we will monitor chat logs and in the unlikely event of inappropriate responses, we will either tighten the guardrails or will pause the study.

As our school partner emphasized the importance of respecting the anonymity and confidentiality of student responses as much as possible, we do not plan for researchers or school staff to initiate any outreach to students or parents based on a student's responses to the intervention or surveys.

18. Participant timeline

Each participant engages with the study across five class periods:

- Class 1: Assent and baseline survey
- Class 2 (1 week after class 1): Intervention group receives growth mindset training; control group does typical classroom activities

- Class 3 (1 week after class 2): Intervention group receives growth mindset training; control group does typical classroom activities
- Class 4 (3 weeks after class 3): Follow-up surveys
- Class 5 (4 weeks after class 4): Follow-up surveys; control group receives shortened growth mindset training; intervention group does other classroom activities

Additional detail is provided in the table below, as well as in Appendix A (Study Procedures).

Participant timeline: Schedule of enrollment, interventions, and assessments.

	TRIAL PERIOD					
	Enrollment		Intervention		Follow-Up	
TIMEPOINT	2.5 Weeks Before Enrollment	Enrollment	1 Week After Enrollment	2 Weeks After Enrollment	3 Weeks After Intervention	7 Weeks After Intervention
ENROLLMENT: Parents informed about study & how to opt-out						
	X					
		X				
		X				
		X				
INTERVENTION/ CONTROL: Intervention group receives growth mindset training Control group receives delayed and shortened intervention						
			X	X		
						X
ASSESSMENTS: Demographic questions						
		X				
		X			X	X

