All statistical analyses will be performed using R. To evaluate intervention effects, we will use a series of mixed-effects regression models implemented via the lme4 package (or comparable tools). Each model will include Time (baseline, 3-week, 7-week), Condition (intervention vs. control), and their interaction (Condition \times Time) as fixed effects, with random intercepts for participants and, where feasible, classroom to account for nesting. The Condition \times Time interaction will test whether outcome trajectories differ between groups over time.

If outcome distributions deviate substantially from normality, we may use generalized linear mixed-effects models with an appropriate link function (e.g., logit, log, or beta) or apply suitable transformations (e.g., rescaling data to a (0,1) interval for beta regression) to improve model fit. All models will be checked for assumptions, including residual distribution and heteroskedasticity.

We will calculate both within-subject and between-subject effect sizes for intervention effects on continuous outcomes. For mixed-effects models, standardized mean differences will be computed from estimated marginal means and pooled residual variance (e.g., using effectsize::t_to_d() or contrasts via emmeans). All effect sizes will include 95% confidence intervals and, when available, Common Language (CL) effect sizes to facilitate interpretation.

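### Random intercepts alone give the surveys at weeks 0, 5 and 9 one variance and one correlation; if variances are similar and the 9-week correlation is the lower one, the SE of the 7-week change contrast is too small

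*Combined protocol and SAP*

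**What the plan says.** Section 27a sets out mixed models "implemented via the lme4 package (or comparable tools"), "with random intercepts for participants and, where feasible, classroom to account for nesting". It names no random slope, serial correlation, unstructured covariance or robust SE. The assumption checks it lists are residual distribution and heteroskedasticity; correlation over time is not among them.

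On the fixed effects it says: "Each model will include Time (baseline, 3-week, 7-week), Condition (intervention vs. control") and their interaction. That "interaction will test whether outcome trajectories differ between groups over time". Section 19 also names this interaction as the primary test. Neither section says whether Time enters as a factor or as a linear term.

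Section 18 fixes the timing: "Class 4 (3 weeks after class 3): Follow-up surveys" and "Class 5 (4 weeks after class 4): Follow-up surveys". Section 10 states the primary objective as the effect "compared to usual classroom activities, from baseline to 3- and 7-weeks post-intervention".

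For effect sizes, section 27a says "standardized mean differences will be computed from estimated marginal means and pooled residual variance", with conversion from t as one example and 95% confidence intervals throughout. Section 27c derives Cohen's d from the t-values of the pooled imputed analyses.

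**The concern.** With a participant intercept and independent residuals, one residual variance sets the SE of every within-student change. Here the gap behind the 7-week change (9 weeks) is about twice either of the others (5 and 4 weeks). The symptom scale in Appendix E asks about the past week, so part of each score may be transient. If similarity between surveys fades with time, the pooled residual variance is too small for the longest-gap change.

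The results at stake are the test of the baseline-to-7-week change by Condition, its 95% CI, and any d computed from its t-value. The first two bear directly on the objective in section 10. How far the primary interaction test is involved depends on the coding of Time.

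**Working it through.** **The plan's own figure.** Section 19 gives a detectable effect of 0.22 for about 430 students, two-tailed alpha 0.05 and 80% power. With z-values 1.96 + 0.84 = 2.80:
- A plain two-group comparison gives 2.80 x sqrt(4/430) = 0.270.
- A change score gives 2.80 x sqrt(4/430 x 2(1 - r)), which is 0.22 at r of about 0.67.
- Baseline adjustment gives 2.80 x sqrt(4/430 x (1 - r^2)), which is 0.22 at r of about 0.58.

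No correlation is stated, so 0.22 can be matched but not verified. It does not tell us which correlations to use below.

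**Timing (section 18).** Class 1 is week 0, Class 2 week 1, Class 3 week 2, Class 4 week 2 + 3 = 5, Class 5 week 5 + 4 = 9. The surveys are at weeks 0, 5 and 9.

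**Formula.** Take equal variances and complete data. For contrast weights c over the surveys, the model variance is proportional to (1 - mean r) c'c and the true variance to c'Rc. For the 7-week change, c = (-1, 0, 1), so

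model SE / true SE = k = sqrt((1 - mean r) / (1 - r at 9 weeks)), and type I error = 2(1 - Phi(1.96 k)).

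Example, with correlations 0.67 / 0.72 / 0.62 (baseline to 3-week, 3-week to 7-week, baseline to 7-week): mean r = 0.67, k = sqrt(0.33/0.38) = 0.93, type I error 6.8%.

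| Assumed correlations | k | Type I error, 7-week change |
|---|---|---|
| No decay | 1.00 | 5.0% |
| Slight: 0.6 + 0.3 x 0.5^gap, i.e. 0.61/0.62/0.60 | 0.99 | 5.3% |
| Moderate: same shares, weekly autocorrelation 0.7 to 0.8 | 0.96 to 0.93 | 6.1 to 6.8% |
| Moderate: 0.67/0.72/0.62 | 0.93 | 6.8% |
| Moderate: 0.70/0.75/0.60 | 0.89 | 8.1% |
| Moderate: 0.65/0.70/0.50 | 0.88 | 8.6% |
| Moderate: exponential 0.90 to 0.95 per week, reliability 0.80 to 0.90 | 0.91 to 0.88 | 7.5 to 8.5% |
| Limiting: same exponential, no measurement error, no stable trait | 0.86 to 0.84 | 9.1 to 10.0% |

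Coverage of the 95% CI is 94.7% in the slight case and 91.4 to 93.9% in the moderate ones.

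**Unequal variances.** The pooled residual variance is the mean variance minus the mean covariance. Take 0.67/0.72/0.62 with the middle-survey SD 10% higher. The mean variance is (1 + 1.21 + 1)/3 = 1.070, the mean covariance is (0.737 + 0.792 + 0.620)/3 = 0.716, and k = sqrt(0.354/0.38) = 0.965, giving 5.9% instead of 6.8%. A middle SD 20% higher gives 4.9%, and one 10% lower gives 7.5%. In the slight case, a middle SD 10% higher gives 4.5%, which is conservative. A steady SD drift of 5 to 10% over the three surveys changes little.

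**The interaction test (equal variances).**
- Time as a three-level factor: the joint 2-df test has type I error of 5.0 to 5.7% over all scenarios.
- Time linear at 0, 5, 9 (weights t - mean t): 5.3% slight, 6.1 to 8.7% moderate, 9.2 to 10.1% limiting. Scored 0, 1, 2, it is the same test as the 7-week change contrast.

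**Simulation.** With 400,000 null trials per scenario and 215 per arm, the 7-week change gave 5.00% (none), 5.24% (slight), 6.76%, 8.09% and 8.48% (the three listed moderate triples, in order). The 3-week change gave 3.61 to 5.02%, and the between-group difference at 7 weeks 4.91 to 5.01%. With each contrast's own variance, all contrasts gave 4.93 to 5.07%.

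A second check added imputation and classrooms. It assumed 430 students, 15 classrooms, ICC 0.05, 6% missing at 7 weeks, six imputations and Rubin pooling, with 4,000 trials. The planned SE gave 4.9% (none), 5.3% (slight), and 6.0%, 8.0% and 8.4% for the same triples. Pooled participant-level SEs gave 4.8%, 5.2%, 4.6%, 5.0% and 4.8%. Neither imputation nor the classroom intercept repairs the SE.

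**The case against.** **The primary test is probably safe.** Sections 19 and 27a list Time by its named occasions, and 27a provides for marginal-mean contrasts. This reads more naturally as a three-level factor. A reader might infer from the word trajectories that Time is linear and that the primary p-value is therefore inflated. No section states linear coding. This objection stands, and it confines the point mainly to one contrast, which is not designated a separate primary test. If that contrast were read only after a significant joint test, both would reject in 2.5% (none), 2.6% (slight), 3.1 to 4.4% (moderate) and at most 5.2% (limiting) of null trials; the plan states no such rule.

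**The size is assumed.** A reader might also infer that the SE is certainly too small. The documents give neither correlations nor variances. If short-lived variation has mostly faded by four weeks, the correlations are nearly flat and the slight case applies. The limiting case is implausible for a six-item self-report. Unequal variances can even reverse the direction. All of this stands.

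**The plan leaves room.** Its list of assumption checks is not closed, and it allows tools comparable to lme4. But nothing commits it to examining or modelling the correlation over time.

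**Conclusion.** The point holds conditionally, as a worthwhile improvement rather than a flaw shown to invalidate the primary result. If variances are about equal and the 9-week correlation is below the mean of the three, the model SE of the 7-week change contrast is about 1% too small under slight decay and about 4 to 12% too small under moderate decay. With constant correlation there is no error.

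With Time as a factor, what is exposed is that contrast, its 95% CI and its t-derived d. Effect sizes from marginal means over pooled residual variance do not take their numerator from the SE. Under the same assumptions, complete-data point estimates and the between-group difference at 7 weeks are not materially affected, and the 3-week change is nominal to slightly conservative. The figures apply to the linear mixed models in the full sample, not to the optional generalized or beta models.

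**What to change.** State in section 27a that Time is a three-level factor. For BFS-Internalizing and the Growth Mindset Scale, then choose one of:

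- (a) an unstructured 3x3 within-student covariance, fitted in a tool other than lmer; or
- (b) the planned mean model with participant-level cluster-robust SEs, and classroom as a fixed effect, for the two change-from-baseline contrasts.

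Compute these SEs in each imputed dataset, pool by Rubin's rules, and base the t-derived effect sizes and CIs of section 27c on them. Either option allows for both decaying correlations and unequal variances.

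The cost is SAP wording and somewhat more analysis work. Option (a) leaves lmer and adds four covariance parameters, which is little with about 430 students. Option (b) needs robust SEs in every imputed dataset. Classroom may move from random to fixed, which changes a planned feature, although a classroom intercept constant over surveys cancels from complete-data change scores. Under the equal-variance scenarios, the 7-week change CI widens by about 1% under slight decay, 5 to 14% under moderate decay and 16 to 19% in the limiting case. It is practically unchanged if there is no decay.

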We have extensively tested the chatbot with thousands of AI-generated and human-generated inputs, including malicious ones, to test its safety and appropriateness in a variety of situations. Given such testing, in combination with the already stringent guardrails of OpenAI GPT-4.1, we feel confident that the content of the bot's responses will be appropriate for a school setting. Nonetheless, we will monitor chat logs after each day of the intervention to ensure that all responses from the bot are appropriate. In the unlikely event of inappropriate responses, we will either tighten the guardrails in advance of the next day's session, or we will pause the study until such changes can be made.

15c. Strategies to improve adherence to intervention/comparator protocols, if applicable, and any procedures for monitoring adherence

To help facilitate the study, a researcher will be available over a video call during study-related class periods, and a local assistant will be physically present to help troubleshoot any technical issues. A script is also prepared for the school teacher to read at the beginning of the study (see Appendix D).

15d. Concomitant care that is permitted or prohibited during the trial

N/A

16. Outcomes

Primary Outcomes:

Change in Behavior and Feelings Survey - Internalizing Subscale (full sample; baseline, 3 weeks, 7 weeks). Trajectories of self-reported symptoms of anxiety and depression from the 6-item (each item rated on a 0-4 scale, with higher ratings indicating more symptoms) Internalizing Subscale of the Behavior and Feelings Survey. Total scores range from 0 to 24, with higher scores indicating more symptoms (BFS; Weisz et al., 2020).

Student Perceived Program Acceptability and Helpfulness (intervention group, post-intervention) - Assessed via the Program Feedback Scale (Schleider et al., 2019). This scale consists of 7 items rated on a 1 to 5 scale, with higher scores indicating greater acceptability and helpfulness.

Secondary Outcomes:

Change in Behavior and Feelings Survey - Internalizing Subscale (**elevated subsample**; baseline, 3 weeks, 7 weeks) - Trajectories of self-reported symptoms of anxiety and depression from the 6-item (each item rated on a 0-4 scale, with higher ratings indicating more symptoms) Internalizing Subscale of the Behavior and Feelings Survey. Total scores range from 0 to 24, with higher scores indicating more symptoms (BFS; Weisz et al., 2020).

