		X			X	X
				X		
					X	X
Growth mindset reflections (intervention group)						

19. Sample size

Our sample size is constrained by the number of available students in the school. We expect about 450 students to be invited to participate (150/students per grade across 3 grades). Assuming an opt-out rate of 5%, we can expect a sample size of about 430 students.

For our primary tests of intervention effects (i.e., mixed effects model examining the time [baseline, 3-week FU, 7-week FU] * condition [Intervention or Control] interaction), an a priori power analysis shows that our sample size can detect effects as small as 0.22 (using two-tailed tests with $\alpha = .05$, $\beta = 0.2$). This effect size is comparable to that detected by a prior single-session growth mindset intervention (Schleider & Weisz, 2018).

20. Recruitment

All students in grades 6-8 at our partner school will be invited to participate.

The school partner was based on strong pre-existing relationships with the research team. The decision to focus on grades 6-8 was made in consultation with the school principal, who believed that these grades would benefit from the intervention while also having flexibility in their curriculum.

Methods: Assignment of interventions

21. Randomization: Sequence generation

21a. Who will generate the random allocation sequence and the method used

The first author will perform the randomization using R.

21b. Type of randomization (simple or restricted) and details of any factors for stratification.

Simple individual randomization (1:1) of participants to intervention or control group.

22. Allocation concealment mechanism

The use of central randomization will ensure that students and teachers cannot determine trial allocation ahead of time. Allocation to the experimental or control groups will take place when class is not in session (between the day of enrollment and the start of the intervention.)

23. Implementation of randomization

As the study procedures are conducted online, assignment of participants to intervention or control groups is done electronically and not by any personnel. Hence no personnel can influence the implementation of the randomized assignment.

24. Blinding

24a. Who will be blinded after assignment to interventions (e.g., participants, care providers, outcome assessors, data analysts)

The intervention will be unblinded for teachers, students and researchers.

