For the mediation analysis, we will use structural equation modeling (SEM) in R (lavaan) to test whether change in Growth Mindset mediates the effect of the intervention on change in BFS-Internalizing. The primary model will specify: Intervention \rightarrow Growth Mindset \rightarrow BFS-Internalizing, with baseline levels of both constructs included as covariates. We will use a latent change score (LCS) mediation model or an observed (composite-score) change model. Indirect effects ($a \times b$) will be estimated using bias-corrected bootstrap 95% confidence intervals, and standardized effects will be reported. Missing data will be addressed using Full Information Maximum Likelihood (FIML) or pooled multiple imputation, consistent with the main analysis. Because indirect effects are typically smaller than direct effects, and given the available sample size ($N \approx 430$), we expect adequate power to detect small-to-moderate indirect effects but limited power for very small ones. Accordingly, this mediation analysis is secondary and exploratory, and findings will be interpreted cautiously.

Transformations

We will examine the distribution of each outcome and apply transformations or generalized linear mixed-effects models as appropriate. For example, if data are heavily right-skewed, we may rescale continuous outcomes to a (0,1) range and fit a **beta-distributed model** to better approximate the observed distribution.

Inference criteria

Two-tailed tests ($\alpha = .05$) will be used.

27b. Definition of who will be included in each analysis and in which group

Participants enter the analysis cohort at randomization, which occurs after assent and baseline measures. Assenting students will be excluded if they do not have the opportunity to complete the baseline measures (e.g., due to interruption or absence) or if they later withdraw consent or assent and ask for their data to be excluded; all others will be included.

All planned analyses will be conducted using the full participant sample (intention-to-treat). We will also conduct subgroup analyses among students with elevated baseline internalizing symptoms—defined as scores ≥ 1 SD above the mean—following established norms for youth mental health measures (e.g., Youth Self-Report; Achenbach & Rescorla, 2001). These analyses will explore whether intervention effects differ when the program is used as a universal versus indicated prevention approach.

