The process above might not require the full class period. Any students who finish early will do an alternative activity assigned by the teacher.

After class, researchers will randomly assign assenting students to control and intervention groups. They will create a table that maps each student’s coded ID to one of three cases: control, intervention, or opt out. This information will be provided to the school to merge with the study roster.

Classes 2 and 3: Growth Mindset Training for Intervention Group

In the next two scheduled periods of technology class, students will be divided into two groups. Students in the intervention group will sit on one side of the computer lab, while students in the control group (and any students who have opted out) will sit on the other side.

Students in the intervention group will do the training program by interacting with an AI chatbot. On the second day of the intervention, following the intervention (or if time runs out, during the last 5 minutes of the class period), students will complete a brief survey to provide program feedback.

Students in the control group (and anyone who opted out) will complete an alternate activity identified by the technology teacher (e.g., a learning activity on the computer). This activity will not take the form of a graded assignment but will be an additional enrichment activity.

Class 4: Follow-up Survey

Three weeks after the training, all participants will be asked to complete a brief follow-up survey (approximately 10 minutes). This activity will occur at the beginning of a normal technology class. As before, the teacher will assist students in entering their coded IDs. Students who have opted out will do an alternate activity.

Class 5: Follow-up Survey and Growth Mindset Training for Control Group

Seven weeks after the training, all participants will be asked to complete a brief follow-up survey (approximately 10 minutes). This activity will occur at the beginning of a normal technology class. As before, the teacher will assist students in entering their coded IDs. Students who have opted out will do an alternate activity.

After the survey, the control group will complete a shortened (15 minute) version of the growth mindset training while the intervention group and opted-out students will do an alternate activity.

Following this class, a printed booklet with all the content from the full version of the training will be provided to all students in grades 6-8.

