Appendix E: List of Measures

- **Demographics (all participants; Baseline/0 Weeks)**
 - How old are you?
 - What grade are you in?
 - What gender do you identify as?
 - (i) Girl, (ii) boy, (iii) I don't identify as just a boy or girl, (iv) Prefer not to say
 - If (iii), optional follow-up: Would you like to tell us more about your gender?
 - What sex were you assigned at birth (e.g., on your birth certificate)?
 - Female, male, prefer not to say, not sure
- **Behavior and Feelings Survey — Internalizing Subscale (all participants; 0 weeks, 3 weeks, and 7 weeks):** brief assessment of anxiety and depression symptoms over the past week.

How much have you had each of the following problems during the past week?

	0 = not a problem	1	2	3	4 = a very big problem
1. I feel sad					
2. I feel bad about myself, or don't like myself					
3. I feel depressed or down					
4. I feel nervous or afraid					
5. I worry about bad things happening					
6. I think sad or scary thoughts over and over again					

- **Program Feedback (immediately post-training):** elicits feedback from the child about the digital program (Schleider et al., 2019).

Please read each statement and select how much you agree or disagree.

	Really Disagree	Disagree	Neutral	Agree	Really Agree
1. I enjoyed the activity					
2. I understood the activity.					
3. The activity was easy to use.					
4. I tried my hardest during the activity.					
5. I think the activity would be helpful to other kids my age.					
6. I would recommend this activity to a friend going through a hard time.					
7. I agree with the activity's message.					

- **Growth Mindset Scale (all participants, all timepoints):** a standard scale to assess growth mindset beliefs (Sigmundsson & Haga, 2024), adapted to lower reading level.

Please read each statement and choose the option that describes you best.

	1 = Not like me at all	2 = Not much like me	3 = Somewhat like me	4 = Mostly like me	5 = Very much like me
1. I know that with effort I can improve my skills and knowledge.					

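### The classroom random intercept drops out of the primary Condition × Time test, so variation shared by a class at one survey stays in the residual: a modest, cheaply removed loss of precision

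*Combined protocol and SAP*

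**What the plan says.** Section 27a (Statistical models) enters Time, Condition and their product as fixed effects, "with random intercepts for participants and, where feasible, classroom to account for nesting". No other classroom term is planned. On the test itself: "The Condition \times Time interaction will test whether outcome trajectories differ between groups over time". Section 19 names this interaction as the primary test and states that "our sample size can detect effects as small as 0.22" with 80% power. Section 27a adds: "Two-tailed tests ($\alpha = .05$) will be used".

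The design facts that bear on the point:

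- Section 21b: "Simple individual randomization (1:1) of participants to intervention or control group". Allocation is not stratified or blocked by class.
- Appendix A, Classes 2 and 3: both arms are in the same lab in the same period, seated on different sides.
- Appendix A, Classes 4 and 5, on the follow-up surveys: "This activity will occur at the beginning of a normal technology class".
- Appendix E, on the Behavior and Feelings Survey (BFS): "How much have you had each of the following problems during the past week".
- Section 27c: missing values are multiply imputed, so each analysed dataset is complete.
- Section 27a also allows a generalized or beta mixed model if the outcome is far from normal.
- Appendix E collects grade but not class section. The roster in Appendix A holds name, coded ID and opt-out status. Sections 26 and 33 have the name-to-ID table deleted after the last survey.

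The documents give no number of classes, intraclass correlation, between-survey correlation or class-by-survey variance.

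**The concern.** The classroom intercept is the plan's only provision for students being taught and surveyed in classes. It describes lasting differences between classes, whereas the primary test compares changes within students, and lasting differences are already removed from a change. The kind of clustering that can reach a change is temporary: a whole class having a bad week, an exam or a noisy session when one survey is taken. The survey procedure and the one-week recall period make such shifts plausible. Simple randomization leaves somewhat uneven arm splits within classes, so the shifts do not cancel exactly between arms and add noise to the contrast. The planned model treats that noise as individual error.

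What is at stake is precision. Section 19 says that the number of students is capped by the school, so the analysis model is one of the few places left to gain any.

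**Working it through.** **1. The plan's detectable effect.** Inputs from section 19: about 430 students (215 per arm), two-sided alpha 0.05, 80% power. A comparison at one time point with SD 1 gives (1.960 + 0.842) × sqrt(2/215) = 0.270. To reach 0.22, a change contrast needs the factor sqrt(2(1 − r)) with r about 0.67: 0.270 × sqrt(2 × 0.332) = 0.220. So 0.22 is attainable but rests on an unstated correlation. I take r = 0.67 below as an assumption, split as participant 0.64, classroom 0.03 and residual 0.33 of a total variance of 1.

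**2. The cancellation.** For student i in class j at survey t, write

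y_ijt = fixed part + b_j (class) + u_ij (student) + c_jt (class-by-survey) + e_ijt.

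The change from baseline to week 7 is

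y_ij7 − y_ij0 = fixed part + (c_j7 − c_j0) + (e_ij7 − e_ij0).

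Both b_j and u_ij are gone; c_jt is not. The planned model has no c_jt, so its variance goes into the residual. What reaches the arm contrast is the sum over classes of (n_1j/n_1 − n_0j/n_0)(c_j7 − c_j0), which is zero only when the arm split is the same in every class.

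**3. Numerical check.** Restricted maximum likelihood (REML) fits to one simulated trial (430 students, 15 assumed classes, class-by-survey variation present, no missing data):

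| Random terms | Week-7 interaction | SE | Residual variance | SE of baseline Condition term |
|---|---|---|---|---|
| Participant | −0.094767 | 0.077445 | 0.3215 | 0.1001 |
| + classroom | −0.094767 | 0.077445 | 0.3215 | 0.0985 |
| + classroom-by-time | −0.0857 | 0.0768 | 0.3109 | 0.0983 |

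The classroom intercept leaves the interaction unchanged to six decimals. It does alter the between-subject term. With follow-ups missing and not imputed, cancellation is only approximate: the SE moves from 0.07945 to 0.07943 at 5% missing, and from 0.08734 to 0.08730 at 15%, where the estimate moves from 0.107 to 0.103.

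**4. Validity.** In 4,000 simulated trials per setting (12 to 18 classes, class-by-survey share 0% to 20% of residual variance), the planned test rejected a true null in 4.3% to 5.8% of trials.

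**5. Size of the gain.** With equal arms the planned SE is sqrt(2/215 × 2 × 0.33) = 0.0784; averaged over simple allocations it is 0.0785. If class-by-survey variance v could be removed completely, the SE would be 0.0785 × sqrt((0.33 − v)/0.33): 0.0761 at v = 0.02 and 0.0723 at v = 0.05. Generalized least squares, which pays for estimating the shifts, falls a little short of that. Power is Phi(0.22/SE − 1.96).

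| v as share of total (of residual, v/0.33) | SE planned | SE with classroom-by-time | Power at 0.22 | Simulated SE, variances estimated, 15 classes | Simulated power |
|---|---|---|---|---|---|
| 0% (0%) | 0.0785 | 0.0785 | 80% to 80% | 0.0784 to 0.0784 | no change beyond simulation error |
| 2% (6%) | 0.0785 | 0.0768 | 80% to 82% | 0.0783 to 0.0768 | 80.9% to 82.4% |
| 5% (15%) | 0.0785 | 0.0730–0.0735 | 80% to 85% | 0.0780 to 0.0733 | 78.8% to 83.4% |

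The simulations used 2,000 trials per setting, so one power figure has a standard error of about sqrt(0.8 × 0.2/2000) = 0.9 points. Results for 12 classes were similar.

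**The case against.** The strongest reply is that nothing here is broken. A reader might infer that clustering has been ignored and that the primary p-value is too small. The documents do not support that for class-wide shifts: students are individually randomized, both arms sit in each session, and the planned test holds its level (step 4). This part of the reply stands in full.

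A second stronger reading is that the classroom intercept is useless. It is not. Section 27a also plans between-subject effect sizes from marginal means, where the intercept matters, and exact cancellation is a property of the linear model that need not hold under the generalized or beta fallback.

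A third is that a large gain is waiting. At a share of 10% of total variance, power would reach about 91%. But 10% of total is about 30% of the assumed within-student residual (0.10/0.33) and over three times the classroom variance assumed here (0.10/0.03). Even 5% is about 15% of the residual and 1.7 times that classroom variance. Nothing in the documents supports shares of that size, and they seem unlikely.

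The validity statement also has a limit. Variation specific to class, arm and survey together, for example from seating the arms apart, would raise the type I error: to 8.7% or 13.3% in simulations that assumed it to be 2% or 5% of residual variance. The documents do not show that it exists, and neither the planned intercept nor the term proposed here would correct it.

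**Conclusion.** The point holds as a matter of precision. In the planned linear model on complete or imputed data, the classroom intercept has no effect on the primary Condition × Time result, so the stated allowance for nesting does not reach it, and class-by-survey variation is counted as error. With a between-survey correlation of 0.67, 430 students and 12 or 15 classes (the correlation and class counts are assumptions), modelling that variation is worth nothing if it is absent, about 2 power points if it is 2% of total variance, and about 5 points if it is 5%. The true share is unknown. Priority is minor to moderate: the planned test is valid against these shifts, but the improvement is close to free and should be settled before outcomes are analysed.

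**What to change.** In section 27a, add a random classroom-by-time intercept, (1 | classroom:time) in lme4 notation, beside the participant and classroom intercepts, for the BFS and the Growth Mindset Scale. Add a sentence saying that this term, and not the classroom intercept, carries the class adjustment for Condition × Time. Enter it as random. When no such variation exists, the simulated SE with the random term was unchanged. Fixed class-by-time effects for 15 classes would raise the SE by a factor of about sqrt(430/(430 − 15)) = 1.018.

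The term needs a class identifier. Have the school supply a class-section label with each coded ID before the name-to-ID table is deleted. If that cannot be done, Grade × Time fixed effects use data already collected, but they remove only shifts common to a whole grade.

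The cost is one model term, one or two sentences, and one extra column from the school. It would also help to state in section 19 the between-survey correlation behind 0.22.
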